#### 4.2 Comparisons of baseline characteristics

First, the distributions of all baseline characteristic variables will be examined using graphical or descriptive statistics to identify any values out of range. When identified, out of range values will be found in the original record, compared and corrected if needed. Second, although by the stratified randomization design, each arm will be distributed across site/city, clinic type (OAT and CHC) and stage of liver disease (cirrhosis vs. no cirrhosis), the success of randomization will be verified by comparing baseline characteristics between the two model of care arms, PN and DOT. Continuous variables will be compared between arms using t-tests or Mann-Whitney tests, and categorical variables will be compared using chi-square or Fisher's exact tests. We will provide only descriptive statistics on the baseline characteristics between arms in a table without reporting of p-values following the CONSORT guideline.

## 5 Analytic plan for the primary Sustained Viral Response (SVR) outcome

### 5.1 SVR Hypothesis

Among participants who *initiate* HCV treatment, rate of SVR at 12 weeks post treatment completion will be higher in the DOT vs. PN arm.

### 5.2 SVR determination process

SVR will be determined for each participant in the ITT sample, and thus for the mITT and PP samples as well. First, the time window for relevant viral load data for determination of SVR is set at between post-EOT (end of treatment) 10 week (or 70 days) and post-EOT 1 year (or 365 days). This time frame is further divided into two windows: the primary time window (post-EOT 70 days to 98 days) and the secondary time window (post-EOT 99 days to 365 days) (Figure 1). SVR status will be declared based on viremia data collected from the medical chart reviews or bio-repository data and classified into the following three categories: Success, Failure, and Undetermined. Detailed algorithm for the SVR determination process within the primary and secondary time windows is described in Figure 2.

Figure 1. Hero Study Post-EOT Timeline for SVR Determination

[figure not shown]
[figure not shown]

Figure 2. SVR Determination Process

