### 7.2 Laboratory Evaluations

HCV Viremia: Blood for HCV viral loads will be sent directly to Quest Diagnostics. Twenty mL of blood will be collected at visits 5, 6, 7, 8, 9, 10, 11, 12, 13, 14, 15, 16 and 17 for HCV viremia testing and archiving. Specimens will be identified only by study ID number or bar-code, and will also be labeled with the name of the research study, the date and time of collection, and the specimen number. Each site will send blood samples directly to Quest. Results which will be entered into the study data system.

Resistance testing: For subjects who fail to achieve SVR or show evidence of reinfection, NS5A/NS5B resistance testing will be performed on the baseline, and either treatment failure visit (unscheduled) or Visit 5 specimens. The second time point will be determined by when treatment failure is first identified. The specimen for “treatment failure visit” will be used if the subject fails treatment during the 12 weeks of treatment, and the specimen for “Visit 5” will be used if the subject fails treatment after the treatment period. All specimens for resistance testing will be shipped to Montefiore CRC, and banked. Batched runs for resistance testing will be run at Monogram.

Biorepository specimen: Blood specimens will be collected at research visits 1, 5, 6, 7, 8, 9, 10, 11, 12, 13, 14, 15, 16 and 17. At Visit 1, twenty mL of blood will be drawn and

stored locally until sent to the study biorepository. A biorepository will be established at Prima Health-Upstate for archiving stored blood for future studies. At all other visits, twenty mL of blood will be drawn and sent to Quest for HCV VL testing and temporary archiving before being sent to Prisma Health-Upstate's Biorepository.

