## 8.7 Unscheduled Visits

Unscheduled visits may occur at any time during the study. They may occur for the following reasons:

- (1) For operational reasons, e.g., a subject may request to reschedule, or to ask questions;
- (2) For SAE related reasons. When interim contacts or visits are completed in response to subject reports of SAEs, study staff will assess the reported event and refer the subject to appropriate medical care. All SAEs will be evaluated and reported as required (Section 9.4);
- (3) If a subject presents to the study site after having missed a scheduled visit (e.g., in response to locator/tracking efforts) on a day that does not fall within a scheduled visit window;
- (4) For other reasons at subject request. All interim contacts and visits will be documented in subjects' study records and on applicable data collection forms.
- (5) If a subject fails HCV treatment. This visit will be solely for collection of 20 mL of blood to be processed and archived by local labs for resistance testing.

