### 3.3 Per protocol analytic sample

This per protocol (PP) analytic sample includes the enrolled study participants who 1) were randomized; 2) initiated treatment; 3) complied with the randomly assigned models of care without cross over any time during the 12-week treatment; and 4) had SVR outcome data (yes vs. no). This sample is referred to as the per-protocol (PP) analytic sample. The PP sample will be a subset of the mITT sample which is in turn a subset of the ITT sample.

The intention-to-treat principle reflects the principle that once the intervention was randomly assigned to a participant, the participant's intervention assignment will not change in the analysis even if s/he crossed over the other intervention during the trial period or did not complete intervention activities. The application of this ITT principle reflects the real-world goal of the HERO study which is to treat all PWID with HCV (i.e., all randomized individuals).

However, as the HERO study was designed as of a pragmatic randomized clinical trial (RCT), the ITT sample will not be used as the primary analytic sample because the outcomes are defined conditions on the initiation. Furthermore, the primary (SVR) and several of the other secondary outcomes (treatment completion, adherence) are only relevant among those who initiated treatment.

**All statistical analyses proposed in the present SAP will be repeated for each analytic sample.** Comparison across the three analytic samples will be compared to assess internal or external validities or limitations of the study findings. In particular, analysis of the secondary ITT sample will provide estimates of milestones along the HCV cascade of care by study arm and in the full sample. All statistical analyses will be conducted using SAS v9.4 and R 3.5 or higher, and a two-tailed significance level of 0.05 will be applied to all testing and confidence intervals.

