### 5.3 Handling undetermined/missing SVR data for primary analysis

#### 5.3.1 mITT analysis

- Primary approach: The undetermined SVR will be treated as SVR failure.
- Secondary approach: The undetermined SVR imputed by a fully specific conditional specification multiple imputation method. This imputation will be made stratified by the study arm. In each arm, overall adherence and the total duration of treatment will be used as predictors of the imputation model. Of note, the imputation will NOT be applied to undetermined SVR due to death; in this secondary approach, deaths will still be treated as SVR failure.

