#### 5.3.2 ITT analysis

- Primary approach: The undetermined SVR will be treated as SVR failure.
- Secondary approach: Any imputation will be not be made to the participants who did not initiate or died during the treatment period. For the other participants, we will use the imputed SVR that was generated for the mITT sample above.

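### Unless SAP Figure 2 says otherwise, viremia found before post-EOT day 70 with no later RNA is Undetermined, so the secondary analyses impute it and per-protocol drops it

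*SAP*

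**What the plan says.** - **Window.** SAP 5.2 states that "the time window for relevant viral load data for determination of SVR is set at between post-EOT" day 70 and day 365; the limits are written as "post-EOT (end of treatment) 10 week (or 70 days) and post-EOT 1 year (or 365 days"). It splits this into "the primary time window (post-EOT 70 days to 98 days) and the secondary time window (post-EOT 99 days to 365 days"). Each participant is classed as Success, Failure or Undetermined. The text says that Figure 2 gives the algorithm within these two windows.
- **Primary approaches.** SAP 5.3.1 and 5.3.2 count Undetermined as failure in both mITT and ITT.
- **Secondary mITT.** SAP 5.3.1 multiply imputes Undetermined within arm, from overall adherence and total treatment duration. There is one exception: "the imputation will NOT be applied to undetermined SVR due to death".
- **Secondary ITT.** SAP 5.3.2 makes no imputation for non-initiators or deaths during treatment. For everyone else, "we will use the imputed SVR that was generated for the mITT sample above".
- **Per-protocol.** Condition 4 in SAP 3.3 requires that the participant "had SVR outcome data (yes vs. no"). SAP 5.3.3 confirms that missing SVR is excluded.
- **Sources of earlier RNA.** SAP 5.2 draws viremia from chart reviews as well as from repository data. Protocol 8.5.1 abstracts chart viremia at treatment weeks 4, 8 and 12.

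**The concern.** A positive RNA result after treatment has ended is direct evidence of failure. On the visible text, a result on post-EOT day 30 does not count towards SVR. If no later sample exists, the person falls into the same category as someone about whom nothing is known.

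The SAP's authors saw that some Undetermined cases are really failures, because they exempt deaths from imputation. No matching exemption is visible for early viremia, and RNA is not a predictor in the imputation model. A known failure can therefore be imputed as a success.

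SAP 3.3 compares results across the three samples to judge the validity of the findings. If these cases are more common under PN, as the trial's hypothesis would suggest, the secondary and per-protocol analyses raise PN SVR more than DOT SVR and understate the difference.

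**Working it through.** **1. Trace one participant**: quantifiable RNA at post-EOT day 30, none on days 70-365, alive, no crossover.

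| Analysis | Rule | Result |
|---|---|---|
| Primary mITT | Undetermined = failure (5.3.1) | Failure |
| Primary ITT | Undetermined = failure (5.3.2) | Failure |
| Secondary mITT | Imputed; only death exempt (5.3.1) | Possible success |
| Secondary ITT | Reuses mITT value (5.3.2) | Possible success |
| Per-protocol | Needs yes/no SVR (3.3, 5.3.3) | Excluded |

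**2. The plan's own figure.** Protocol 11.10 and SAP 5.5 give 89% vs 80% as the detectable difference, with 10% of the predictor's variation explained by covariates. I used a two-proportion test, two-sided 0.05, with effective n = n × (1 − 0.10). At 270 per arm (243 effective) power is about 78.5%, and the minimum detectable difference is 9.2 points (OR 2.06). At the SAP's 300 per arm (270 effective) power is 82.6% and the minimum is 8.75 points. The figure reproduces closely and is used as the baseline.

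**3. Per-protocol.** Let s be SVR with these cases counted as failures, and e the share of the arm made up of such cases. After exclusion, SVR = s / (1 − e). I ignore other exclusions. The documents do not give e, so I assume a fraction f of failures (20% of PN, 11% of DOT).

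| f | PN | DOT | Difference |
|---|---|---|---|
| 10% | 0.80/0.980 = 81.6% | 0.89/0.989 = 90.0% | 8.4 |
| 20% | 0.80/0.960 = 83.3% | 0.89/0.978 = 91.0% | 7.7 |
| 30% | 0.80/0.940 = 85.1% | 0.89/0.967 = 92.0% | 6.9 |

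With 300 per arm, f = 10% means about 6 PN participants (0.02 × 300) and 3 DOT participants (0.011 × 300).

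The shrinkage depends on PN having more such cases. With e = 3% in both arms the difference is 0.09/0.97 = 9.3 points. With 5% in PN and 1% in DOT it is 0.89/0.99 − 0.80/0.95 = 5.7 points.

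**4. Imputation.** Imputed SVR = s + e × π, where π is the mean imputed chance of success. The documents do not give π. I simulated one arm of 300 with SVR about 78%. Success followed logit = −3.2 + 0.045 × days + 1.5 × adherence. Of the arm, 80% had 84 days of treatment and the rest 7-83; adherence had mean 0.78 and SD 0.15. Up to 8 failures were set to undetermined and imputed from both SAP predictors. All these values are assumptions. π was about 0.32 when those failures had at most 28 days of treatment, 0.40 with at most 56 days, and 0.67 with up to 84 days.

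With the same π in both arms, the difference is 9 − (e_PN − e_DOT) × π:
- f = 10%: 9 − 0.9 × 0.32 = 8.7, down to 9 − 0.9 × 0.67 = 8.4 points
- f = 20%: 9 − 1.8 × 0.32 = 8.4, down to 9 − 1.8 × 0.67 = 7.8 points

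**5. How often can this arise?** Protocol 8.6 times visits from treatment start, with study RNA at weeks 24, 36, 48 and 60. For a 12-week completer, subtracting 84 days gives post-EOT days 84, 168, 252 and 336. All lie inside days 70-365. A case arises only if the participant misses all four visits and has no in-window chart RNA.

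**6. Against the primary estimate.** If 7% of each arm are lost for other reasons (assumed) and scored as failures, the primary approach expects 0.93 × 9 = 8.4 points.

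**The case against.** The strongest objection is that Figure 2 separates Failure from Undetermined and may already handle this case. That cannot be excluded, so the point is conditional. Two things in the text weigh against it. Figure 2 is described as working within the two windows, and day 30 lies in neither. Also, SAP 5.3.1 speaks of SVR left undetermined by death, so even some intended failures leave the algorithm as Undetermined and need an explicit exemption.

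Three stronger readings are tempting, and the documents do not support them:

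- **That these failures would mostly be imputed as successes.** This follows only if treatment duration is left out of the imputation model, and the SAP names it as a predictor. With duration included, success is the likelier imputed result only after a near-complete course.
- **That the checks would contradict a true primary result.** At f = 10% they give 8.4 to 8.7 points against an expected primary of about 8.4 (steps 3, 4 and 6). Even at f = 30% the direction is unchanged. No figure in the documents supports shares of 10-30%, and the visit calendar suggests fewer.
- **That failure noted during treatment should be carried forward in the same way.** Protocol 7.2 mentions a specimen that "will be used if the subject fails treatment during the 12 weeks of treatment", and Protocol 8.7 lists an unscheduled visit: "If a subject fails HCV treatment. This visit will be solely for collection of 20 mL of blood". That blood is for resistance testing. Neither section defines virologic failure, so a rule cannot rest on them.

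It also stands that excluding missing SVR from per-protocol is explicit and deliberate. The gap is that an observed failure may be treated as missing.

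**Conclusion.** The point holds as a conditional gap in the secondary and per-protocol analyses only. Unless Figure 2 classes it as Failure, quantifiable RNA after end of treatment but before day 70, with no RNA in either window, is imputed in secondary mITT and ITT and excluded from per-protocol. Both primary approaches already score it as failure.

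The effect is probably small: about 0.6 points off the 9-point per-protocol difference if 10% of failures are of this kind, and about 1.3 points at 20%. Imputation costs the same or less under the assumptions of step 4. These sizes rest on the plan's 80% and 89%, on the same fraction of failures being affected in each arm, and on shares that the documents do not give. The change is still worth making, because an observed failure should have no chance of counting as a success.

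**What to change.** - **SAP 5.2**, add: *A participant with no viral load in the primary or secondary window, but with quantifiable HCV RNA on any chart or study sample at post-EOT days 1-69, is classed as Failure (determined).* If Figure 2 already does this, say so in the text, because the window rule reads otherwise.
- **SAP 5.3.1 and 5.3.2**: exempt these participants from imputation alongside deaths, and keep them as observed failures when fitting the imputation model.
- **SAP 3.3**: let this classification satisfy condition 4.
- Leave the rule unchanged wherever an in-window RNA exists.

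The cost is a few sentences, and chart review already supplies the data. There is one small downside: a low-level early result that would later have cleared could be scored as failure. Requiring quantifiable RNA limits this.

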### 5.3 Handling undetermined/missing SVR data for primary analysis

#### 5.3.1 mITT analysis

- Primary approach: The undetermined SVR will be treated as SVR failure.
- Secondary approach: The undetermined SVR imputed by a fully specific conditional specification multiple imputation method. This imputation will be made stratified by the study arm. In each arm, overall adherence and the total duration of treatment will be used as predictors of the imputation model. Of note, the imputation will NOT be applied to undetermined SVR due to death; in this secondary approach, deaths will still be treated as SVR failure.

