## 11.7 Missing data analysis

In order to not compromise internal or external validity of our study results, every effort will be made to minimize missing data that could occur due to missed visits or subject attrition. A maximum 10% subject attrition rate is anticipated during the first 24-week intervention period considering a real-world situation that withstands a tight control. However, the missing outcome data rates will depend on the outcome definition whereas most analyses will use baseline characteristics as covariates that will thus have negligible missing data rate.

The primary analysis will be based on available data without missing data imputation; however, we will conduct variety of missing data imputation methods for sensitivity analyses. Depending on the clinical nature of outcome, worst scenario imputation or, if deemed more relevant, mean imputation methods will be considered. In addition, fully specific conditional specification multiple imputation methods will also be applied, which are applicable to non-ignorable missing data.

Characteristics of patients who are lost to follow-up will be compared to those that remain in the study to assess the degree of any selection bias due to attrition, and the analysis results of the different types of imputed missing data will be compared to the primary analysis results. In particular, variability of the coefficients of primary predictors across the different imputation methods will be assessed to evaluate robustness of the findings. If the changes in the coefficients are greater than 15% from those of the primary analysis, we will limit the generalizability, internal and external validity of our findings, which we nevertheless do not believe will occur if attrition rates are less than 25%.

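### The SAP replaces the Protocol's available-case primary analysis of SVR with missing = failure without recording the change, and two missing-data statements in Protocol 11.7 are unsupported

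*SAP*

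**What the plan says.** Protocol 11.7 covers all outcomes, so it includes SVR. Its rule is: "The primary analysis will be based on available data without missing data imputation". Imputation comes in only as sensitivity analysis: "Depending on the clinical nature of outcome, worst scenario imputation or, if deemed more relevant, mean imputation methods will be considered", and multiple imputation by fully conditional specification is added. Of that method the Protocol says: "which are applicable to non-ignorable missing data".

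The same section sets a robustness test. "If the changes in the coefficients are greater than 15% from those of the primary analysis", the claims to validity and generalisability are to be limited, an outcome "which we nevertheless do not believe will occur if attrition rates are less than 25" per cent. It anticipates at most 10% attrition over the first 24 weeks.

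SAP 5.3.1, for the mITT sample, states: "Primary approach: The undetermined SVR will be treated as SVR failure". SAP 5.3.2 repeats that rule for the ITT sample. Multiple imputation is the secondary approach. Of the imputation the SAP says: "This imputation will be made stratified by the study arm", and that "overall adherence and the total duration of treatment will be used as predictors of the imputation model". Deaths are not imputed and stay failures. The per-protocol sample (SAP 3.3 and 5.3.3) contains only participants with an observed SVR, and it also excludes crossovers.

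**The concern.** Both documents define the primary SVR analysis on participants who were randomised and took at least one dose (Protocol 11.2, SAP 3.1), yet they treat a participant without an SVR result differently. The Protocol leaves that person out; the SAP counts a failure. The available SAP text neither refers to Protocol 11.7 nor gives a reason. The Protocol's own primary analysis has no counterpart in the SAP, because the per-protocol analysis is the nearest and it drops crossovers as well.

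Three things are at stake. A reader who compares the report with the Protocol will find a different primary analysis and no explanation. The 15% test, which governs what may be claimed about validity, rests on an expectation that ordinary amounts of missing data could defeat. And a reader of 11.7 would believe that the imputation protects against missingness that depends on SVR itself.

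**Working it through.** **Inputs.** SVR 80% in PN and 89% in DOT, 10% of predictor variation explained by covariates, two-sided 0.05 and 80% power (Protocol 11.4 and 11.10; SAP 5.5). 300 per arm, or 270 after 10% attrition (Protocol 11.4). Neither document gives the undetermined share, and the determination algorithm (SAP Figure 2) is not readable in the text, so shares are assumed. The 80% and 89% are taken as rates among determined participants, also an assumption.

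**The plan's own figure.** Effective n = 270 × 0.90 = 243 per arm. Power = Φ{[d√n − 1.96√(2p̄(1−p̄))] / √(p₁(1−p₁)+p₂(1−p₂))}. At 89% vs 80% this is Φ{(0.09 × 15.59 − 1.96 × 0.512)/0.508} = 78.5%. The difference detectable at 80% power is 9.16 points (OR 2.06), so the stated 9 points and OR 2.1 reproduce to rounding. Exactly 89% vs 80% gives OR (0.89/0.11)/(0.80/0.20) = 2.02, log-OR 0.704.

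**Moving from one primary rule to the other.** If shares m(DOT) and m(PN) are undetermined and counted as failures, the rates become 0.89(1 − m(DOT)) and 0.80(1 − m(PN)).

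| Undetermined DOT / PN | Rates DOT / PN | OR | Change in log-OR |
|---|---|---|---|
| 0 / 0 | 89.0% / 80.0% | 2.02 | reference |
| 2% / 2% | 87.2% / 78.4% | 1.88 | −10% |
| 5% / 5% | 84.6% / 76.0% | 1.73 | −22% |
| 10% / 10% | 80.1% / 72.0% | 1.57 | −36% |
| 25% / 25% | 66.8% / 60.0% | 1.34 | −59% |
| 8% / 12% | 81.9% / 70.4% | 1.90 | −9% |
| 7% / 13% | 82.8% / 69.6% | 2.10 | +5% |
| 12% / 8% | 78.3% / 73.6% | 1.30 | −63% |

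With equal shares, the 15% limit is passed at m = 3.1% on the log-OR scale (the scale of the logistic coefficient) and at 5.2% on the OR scale. With the SAP rule as reference, the available-case log-OR at 10% is 0.704/0.448 − 1 = 57% larger.

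**The non-ignorable claim.** The SAP imputation uses adherence and treatment duration within arm and has no term that shifts the imputed rate away from that of comparable determined participants. It therefore assumes missing at random given those two variables within arm. An example shows what this can miss. Suppose that, among participants alike on both predictors, DOT loses 5% of successes and 50% of failures while PN loses 10% of each; 10% are then missing in each arm. Observed DOT successes and failures are 0.89 × 0.95 = 0.8455 and 0.11 × 0.50 = 0.055, a rate of 93.9%; PN stays at 80%. Imputation at the observed rates gives OR 3.84 against a true 2.02. If the same selection acts in both arms, the OR is not distorted, so the bias depends on the pattern.

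**What a delta-adjusted run would show.** Take 300 per arm, 10% undetermined, an unadjusted two-proportion z test, and ignore between-imputation variance. Imputing at the determined rates gives 89% vs 80%, z = 3.05, p = 0.002. Now hold PN at 80% and let the undetermined DOT participants have SVR x, so that DOT overall is 0.89 × 0.90 + 0.10x. p reaches 0.05 when DOT overall is 86.0%, that is, x = (0.860 − 0.801)/0.10 ≈ 59%. No planned analysis looks at this range between the missing-at-random model and the failure extreme.

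**The case against.** The strongest reply is that nobody following the SAP is left in doubt. Section 5.3 is specific to SVR and names one primary and one secondary approach. SAP 2 ties both statisticians to that plan, and SAP 1 says that it was approved before outcome data collection and cleaning were complete. All of this stands. A reader might infer that the primary rule is wrong, ambiguous or chosen after seeing results; the documents support none of these. What remains is an undocumented departure. Because the SAP's title page was not available, its absence can be asserted only for the text supplied.

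A second reply concerns the 15% limit. The 25% sentence is worded as a belief, and it is about attrition. SAP 5.2 accepts chart or biorepository viremia up to 365 days after treatment ends, so a participant lost to visits may still have an SVR result. Worst-scenario imputation is only to be considered. More undetermined results in PN than in DOT are also plausible, given the hypotheses on adherence and completion, and at 8%/12% or 7%/13% the shift stays under 15%. This stands too. It would be wrong to infer that any small undetermined share must breach the limit. But 11.7 offers nothing in support of its expectation, and equal shares or more loss in DOT defeat it.

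Third, the non-ignorable wording occurs only in the Protocol, and the SAP keeps deaths as failures. That narrows the point without removing it, since all other undetermined results are imputed with no shift.

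A reader might finally infer that the 9-point power figure in SAP 5.5 fails under the new rule. That does not follow. If 80% and 89% already count undetermined as failure, power with 300 per arm and 10% explained variation is about 83%.

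**Conclusion.** The concern holds as a matter of documentation and of two unsupported statements; it is not a fault in the SAP's primary rule. It should be fixed, but it does not threaten the design.

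The change of primary rule is certain from the text. Its size depends on the undetermined share and its split by arm, which the documents do not give. With equal shares and the planning rates read as rates among determined participants, the log-OR falls by 22% at 5% undetermined and by 36% at 10%, the highest attrition that the Protocol anticipates. Other splits run from little change to −63% in the cases shown.

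The 25% expectation is therefore unsupported rather than refuted for every pattern. The non-ignorable statement is wrong for the imputation as specified: apart from the fixed missing = failure extreme, no planned analysis addresses missingness that depends on SVR.

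**What to change.** 1. Add a dated note to SAP 5.3 that 5.3.1 supersedes Protocol 11.7 for SVR, with the reason. Align 11.7 at the next amendment.
2. Keep the available-case mITT analysis as a named sensitivity analysis.
3. In Protocol 11.7, delete the 25% expectation, or qualify it by the methods compared and the pattern of undetermined results by arm.
4. Replace the non-ignorable statement with the actual assumption: missing at random given adherence and treatment duration within arm, with deaths kept as failures. Add a delta-adjusted (tipping-point) run, varied separately by arm, on the imputation already planned.

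**Cost.** No new data, and no change to sample size or to the SAP's primary rule. There is a little more analysis work. The Protocol wording needs ethics board approval at each institution before use (Protocol 14.2), which is why the SAP note should come first.
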